Cortisol response to the TSST was examined as a function of group status (supplementation versus placebo) at baseline, 24 and 30 weeks of gestation by repeated measures analysis of variance, using a Greenhouse-Geisser correction to account for lack of sphericity. Time of day was significantly associated with initial cortisol levels at baseline, but not at 24 and 30 weeks, thus time of day was controlled in all analyses involving cortisol levels at baseline. Cortisol levels before and after the TSST did not vary as a function of supplementation at baseline or at 24 weeks. At 30 weeks, cortisol levels over time significantly differed as a function of supplementation (F [1.78, 83.85] = 6.24, p = .004, cohen's d = .76). As shown in Figure 3, women who received placebo had higher levels of cortisol upon arrival to the lab compared to women receiving

omega-3 supplementation. Levels for women receiving placebo were characterized by a relatively steep decline, whereas levels for women receiving omega 3 supplement evidenced a slight increase in response to the stressor, on average, followed by decline during the period of recovery. To further probe the differences in levels upon arrival to the laboratory, the two groups were compared at baseline, 24 weeks, and 30 weeks of gestation. As shown in Figure 4, cortisol levels upon arrival to the lab were similar for the two groups at baseline, but diverged over time such that by 30 weeks of gestation women who received placebo had levels that were on average 20% higher than women receiving supplement (F [1.74, 74.63] = 3.51, p = .041, cohen's d = .56).

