Results from the present study provide preliminary evidence that changes in prenatal nutrition may be one way to interrupt the suboptimal prenatal programming of the fetus developing in the context of high levels of maternal stress. Pregnant women living in high stress, low-income, urban environment, receiving a fatty acid supplement reported lower levels of perceived stress than women who received placebo, despite a lack of change in exposure to stressors. Moreover, the reduction of perceived stress was independent of depression, which was not associated with fatty acid supplementation. In fact, evidence from the present study suggests that DHA supplementation does affect the functioning of the HPA-axis by modulating response to a social stressor. This effect was demonstrated primarily via a lower cortisol response to arriving at the laboratory. By 30 weeks of gestation, participants who received DHA supplementation had lower levels of cortisol upon arrival to the laboratory, and on average demonstrated a slight increase in cortisol in response to the stressor, a pattern typically observed late in pregnancy (Nierop et al., 2006; de Weerth et al., 2005). In contrast, participants who had received placebo evidenced high levels of cortisol upon arrival to the laboratory, followed by a steep decrease in cortisol levels during and after exposure to the TSST. One interpretation of this pattern is that an exaggerated response to anticipatory stress leads to a less flexible response to the stressor. The high levels of cortisol upon arrival to the lab followed by a lack of responsiveness to the stressor has been described as a pattern of dysregulated HPA axis functioning associated with depression both in adults (Burke et al., 2005) and children (Suzuki et al., 2013). Lack of cortisol response to a social stressor also has been observed among adults reporting high levels of early life adversity, especially females (Lovallo, 2013). DHA supplementation appears to protect pregnant women living in low-income environments from manifesting this type of dysregulation.

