There are two reasons for our focus on African American women. First, as described above, African American women are disproportionately represented among families living in inner-city poverty and have the highest rates of suboptimal birth outcomes in the U.S. (Giscombé & Lobel, 2005). Second, there are racial differences in cortisol reactivity to

stress and pregnancy (De Santis et al., 2007; Glynn et al., 2007; Wilcox et al., 2005) and in the genes regulating cortisol (Baerwald et al., 1999). Given the scope of the proposed study and the potential to generate data that can be translated into reductions in health disparities, we chose to study African Americans only, but acknowledge that it will be important to test racial and ethnic differences in maternal and infant response to DHA supplementation during pregnancy.

Women will be randomly assigned to receive the omega-3 nutritional supplement (n = 112) or a corn and soybean oil placebo (n = 56) beginning at enrollment and up through the end of pregnancy. In the proposed design we allocate the number of participants to groups to optimize power to test the hypotheses. We expect greater variability in the independent measure (i.e. DHA level) and dependent measures (e.g., stress reactivity) in participants in the experimental group than those in the control group given anticipated differences in uptake and metabolism. Thus, we plan to enroll a higher number of participants in the experimental group than in the control group to adequately capture that variability (Cox, 1958). Participants and investigators will be blinded to the group to which they have been assigned. Treating clinicians will identify demographically eligible participants who will be contacted by research staff for further screening. Participants who meet the inclusion and exclusion criteria will then be scheduled for the baseline visit.

Participants will be reimbursed on an accelerated schedule with \$100 for their first visit and an increase in payments by \$25 for each subsequent visit, ending with a \$250 payment for the last post-partum visit. Participants will receive incentives in between visits including water bottles, tote bags, newborn t-shirts, etc. They also will be reimbursed with \$10 to cover travel costs for each visit.

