Measure	Variables		16-20 wks	24-30 wks	34-36 wks	1 month	4 months	9 months
Maternal Psychosocial Stress								
Perceived stress	Perceived stress Total score from PSS		1	>	>	>	>	1
Life events	Life events Total score from DLC		1	1	1	1	1	1
Depressed mood		1	1	1	1	1	1	1
Anxiety Total score from STAI		/	1	1	1	1	/	1
Maternal Stress Response								
Reactivity to TSST	Cortisol; HR, BP	>	1	>	>			
DHA Levels								
Blood draw	DHA levels in red blood cells	>	1	1	1			
Maternal Inflammatory Markers								
Blood draw	CRP; IL-6; TNF-α	>	1	>	>			
Infant Outcomes								
Birth	Birth weight, gestational age, Apgar, meconium					1		
Neurodevelopmental functioning	NBAS, BSID					1	1	1
Stress reactivity	Cortisol response to NBAS, FFSF					>	>	1
Temperament	IBQ; IBQ-R – short form						1	1

Table 1. Overview of main study variables

Hypotheses and Analyses

Hypothesis 1. DHA supplementation will improve maternal health during pregnancy among African American women living in urban poverty. Women who receive DHA supplementation will report lower levels of self-reported perceived stress over time, despite a lack of change in exposure to environmental stressors. Inflammatory markers including C-reactive protein (CRP), IL-6, TNF-α will be lower among women receiving DHA supplementation compared to placebo. To test for significant differences in perceived stress and inflammatory marker levels we will use repeated measures ANOVA (rmANOVA) with supplement group as the between-subjects factor and visit as a within-subjects factor. The interaction between group and time will be of particular interest. A Greenhouse-Geisser sphericity adjustment (Geisser & Greenhouse, 1958) will be employed. If any of the dependent measures exhibit a non-normal distribution (e.g. CRP), then a suitable data transformation will be used. Changes over time in prenatal levels of depression and anxiety will also be assessed using rmANOVA. Scatter plots and box plots of the data will be used to further explore these relationships. Plots of the data also will be examined to detect nonlinear time effects in addition to using orthogonal polynomial contrasts to formally test for quadratic and cubic effects. The association between change in DHA levels in the blood from baseline to the last prenatal visit and change in perceived stress will be examined using linear regression models.

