Response to a controlled stressor including cortisol, blood pressure, and heart rate will be better modulated among women receiving DHA supplementation than among women who do not, as demonstrated by a lower peak response and more rapid recovery to baseline. Differences in stress reactivity (i.e., cortisol levels, blood pressure, and heart rate) will be tested using two complementary approaches. First, we will use rmANOVA with supplement group as the between-subjects factor and timing of measurement (e.g. 20 minutes and 5 minutes pre-TSST, and 20, 40, and 50 minutes post-TSST for cortisol) as the within-subjects factor for each of the 4 prenatal visits separately. The interaction between group and time will be tested. For further interrogation of these changes, a random intercept, random slope mixed-effects model will be fit and results compared to the rmANOVA results. Second, the area under the curve (AUC) will be calculated for each participant at

each visit. Since primary interest is in assessment of changes over time, the AUC_I (area under the curve with respect to increase) will be used (Pruessner et al., 2003). Differences in these AUCs will be tested using rmANOVA with supplement group as the between-subjects factor and visit as the within-subjects factor. The interaction between group and visit will also be included to explore whether the magnitude of the difference between the groups is affected by the length of DHA supplementation. A Greenhouse-Geisser sphericity adjustment will be employed in both rmANOVA analyses. For further exploration of the patterns over time, a cluster analysis using the AUCs at each visit will be performed, and the association between the "change groups" formed from this cluster analysis and supplement group will be determined using a chi-square or Fisher's exact test. Log-transformed cortisol values will be used if appropriate. Also, time of collection and prenatal depression and anxiety will be controlled for in these analyses if needed.

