Power Calculations for Hypothesis 1. In this study with 108 participants in the supplement group and 54 in the placebo group, there will be >90% power to detect a difference in stress levels, at any particular visit, of the same magnitude as that observed in our preliminary study at 30 weeks (27.5+/-3.4 vs. 29.3+/-3.1), using a two-sided test at the 0.05 significance level. Additionally, with 162 participants, there will be 80% power to detect a correlation of 0.22 between changes in DHA levels in the blood versus changes in perceived stress. For the cortisol response to the TSST, there will be >95% power to detect a difference in AUCs at a given visit of the same magnitude as that found in our preliminary study at 30 weeks (-4.5+/-3.9 vs. -8.1+/-6.1; negative values indicating net decreases rather than increases), using a two-sided test at the 0.05 significance level.

Hypothesis 2. DHA supplementation during pregnancy will improve infant birth and developmental outcomes among African American women living in urban poverty.

Infants of mothers who receive DHA supplementation will have longer gestations, higher birth weights, more optimal neurodevelopmental outcomes as measured by the NBAS and Bayley Scales of Infant Development, and more optimal maternal reports of temperament in comparison to infants whose mothers did not receive DHA supplementation. We will use ANOVA (e.g. birth weight) or rmANOVA (e.g. NBAS) to test for significant differences between treatment groups. For categorical infant outcomes, such as pre-term birth or low Apgar scores, logistic regression will be employed. We will also test the association between level of DHA in blood at the last prenatal visit and/or change in DHA levels from baseline and infant outcomes using linear (e.g. birth weight or change in NBAS) or logistic (e.g. pre-term birth) regression.

Transformations of the continuous dependent measures will be performed to stabilize the variance across groups if needed.

Infants of mothers who received DHA supplements will demonstrate more modulated cortisol response to the NBAS and still-face paradigm, with a lower peak response and a steeper slope from peak to recovery, in comparison to infants whose mothers did not receive DHA supplementation. Analyses will be performed as described for Hypothesis 1.

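### The 2:1 allocation is justified partly by greater stress-reactivity spread in the DHA arm, the pilot cortisol AUC SDs point the other way, and the planned AUC test pools variance across unequal arms under either premise

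*Combined protocol and SAP*

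**What the plan says.** **Allocation.** The Participants section assigns 112 women to supplement and 56 to placebo, states that the split is meant to optimise power, and gives as reason: "We expect greater variability in the independent measure (i.e. DHA level) and dependent measures (e.g., stress reactivity) in participants in the experimental group". The expectation is attributed to differences in uptake and metabolism.

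**Pilot figures.** Power Calculations for Hypothesis 1 uses 108 and 54 women and claims more than 95% power for the AUC difference seen in the pilot at 30 weeks. After a leading minus sign, the pair reads "4.5+/-3.9 vs. -8.1+/-6.1; negative values indicating net decreases rather than increases". The arms are not labelled there. The pilot narrative (Preliminary support for hypotheses) says that "participants who had received placebo evidenced high levels of cortisol upon arrival to the laboratory, followed by a steep decrease in cortisol levels", which places -8.1 +/- 6.1 with placebo. The other pilot pairs also list supplement first.

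**Analysis.** Under Hypothesis 1: "Differences in these AUCs will be tested using rmANOVA with supplement group as the between-subjects factor and visit as the within-subjects factor". Four nearby provisions might be read as safeguards:
- the Greenhouse-Geisser adjustment;
- for cortisol, "Log-transformed cortisol values will be used if appropriate";
- for the samples within a visit, "a random intercept, random slope mixed-effects model will be fit and results compared to the rmANOVA results";
- for Hypothesis 1 outcomes generally, "If any of the dependent measures exhibit a non-normal distribution (e.g. CRP), then a suitable data transformation will be used".

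A clause on stabilising variance between groups does exist, but it sits under Hypothesis 2, with the infant outcomes.

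**The concern.** The plan itself expects the arms to differ in spread and makes them unequal in size, then names a test that assumes equal spread. With equal arms a pooled-variance comparison tolerates unequal SDs well; at 2:1 it does not. The direction of the error depends on which arm varies more, and the rationale and the pilot disagree on that.

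None of the provisions listed above is tied to between-arm variance. Greenhouse-Geisser deals with the within-woman covariance pattern. The general transformation is triggered by non-normality. The log option has no variance trigger; it acts on the cortisol values and cannot be applied to AUC_I itself, whose mean is negative in both pilot arms. The random-slope model is described for samples within a visit, not for AUC, and states no arm-specific covariance.

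At stake are the p-values and intervals of one of the two planned stress-reactivity analyses, the one on which the cortisol power statement rests.

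**Working it through.** **Inputs.** From Power Calculations for Hypothesis 1: n = 108 (DHA) and 54 (placebo), pilot SDs 3.9 and 6.1, difference -4.5 - (-8.1) = 3.6, two-sided 0.05. Between-visit correlations (0.3, 0.5, 0.7) and early-visit SDs are not in the document and are assumptions.

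**1. The plan's own figure.** Pooled variance = (107 x 3.9² + 53 x 6.1²)/160 = (1627.5 + 1972.1)/160 = 22.50, so the pooled SD is 4.74. Pooled SE = sqrt(22.50 x (1/108 + 1/54)) = 0.79. Then 3.6/0.79 gives power of 99.5%. Welch's test gives 97.4% on about 75 degrees of freedom. The claim of more than 95% is reproduced.

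**2. Single visit (illustration only).** True SE = sqrt(3.9²/108 + 6.1²/54) = sqrt(0.141 + 0.689) = 0.91.
- Pilot SDs: 0.79/0.91 = 0.868, so the nominal 5% test rejects at 2 x [1 - Φ(1.96 x 0.868)] = 8.9%, and coverage is 91.1%.
- Reversed SDs: pooled SE 0.912, true SE 0.791, ratio 1.152, giving 2.4%.
- Welch's test simulates at 5.0% in both cases.

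**3. Group effect over four visits.** This test equals a pooled comparison of each woman's four-visit mean. Example: correlation 0.5, SD 3.9 in both arms at three visits, then 3.9 against 6.1 at the last.
- DHA: variance of the mean = (4 x 15.21 + 12 x 0.5 x 15.21)/16 = 9.51.
- Placebo: (3 x 15.21 + 37.21 + 6 x 0.5 x 15.21 + 6 x 0.5 x 3.9 x 6.1)/16 = 12.49.
- Pooled variance = (107 x 9.51 + 53 x 12.49)/160 = 10.5; pooled SE 0.540.
- True SE = sqrt(9.51/108 + 12.49/54) = 0.565; ratio 0.956; type I error about 6.1%.

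**4. Four-visit simulation** (normal, complete data, Greenhouse-Geisser on group-by-visit; ranges cover the assumed correlations and early-visit SDs):

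| SD pattern | Group | Group-by-visit |
|---|---|---|
| Pilot SDs, last visit only | about 5.5-6.5% | about 5-8% |
| Pilot SDs, three of four visits | up to about 8% | up to about 11% |
| Reversed, last one to three visits | about 2.5-4.5% | about 1.5-5% |
| Placebo/DHA SD ratio 1.25 | 5.1-6.6% | 5.3-7.6% |

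With equal SDs the rmANOVA holds its level (4.7-5.1%).

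**5. The proposed model.** With separate covariance by arm, under the pilot, reversed, equal and 1.25-ratio patterns, type I error is 4.7-5.2% for group. For group-by-visit it is 4.8-5.3% with Kenward-Roger and 5.1-5.7% with Satterthwaite degrees of freedom.

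**6. How firm are the pilot SDs?** The reported "F [1.78, 83.85] = 6.24, p = .004, cohen's d = .76" implies 83.85/1.78 + 2, or about 49 women. The variance ratio is (6.1/3.9)² = 2.45. At an assumed 33/16 split, the F-test p is about 0.03, or 0.10 after Bonferroni for the three pilot SD pairs in the document. If the data are lognormally skewed, equal true SDs produce an SD ratio this extreme (6.1/3.9 = 1.56) in 11.5-22% of samples.

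**The case against.** The contradiction is thin. The Participants section states an expectation and claims no pilot support for it. Against it stands one pair of SDs from one visit and about 49 women with three saliva samples, with arm labels that must be inferred. Stress reactivity also covers heart rate and blood pressure, for which no SDs are given. The other pilot pairs are mixed: perceived stress 3.4 against 3.1 leans the plan's way and birth weight 480 against 549 g leans against it. The Maternal Stress Response section changes acclimation and sampling, so the pilot SDs may not carry over. All of this stands, and it limits the size of the point. It does not remove it, because the pooled test also miscalibrates if the plan's own expectation is correct.

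Logging the cortisol values could narrow the gap: pilot SD rises with the size of the mean, as such data often do. That is possible, but no log-scale case was modelled, and the option has no stated trigger.

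The top figures need divergence at three of four visits. The pilot reported group differences in cortisol response only at 30 weeks, so the last-visit figures are the better guide.

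The arm-specific model has 20 covariance parameters, ten of them estimated from 54 women, and was checked only on complete normal data, whereas the plan carries last observations forward. This stands, and the fix must address it.

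**Conclusion.** The point holds in a limited form. The stress-reactivity part of the allocation rationale runs against the only arm-specific reactivity SDs given, and the AUC_I test has no protection against unequal arm variances in either direction. The likely size is a fraction of a point to about three points of type I error if pilot SDs appear at the last visit only, and more if they appear earlier. These figures rest on normal complete data and on assumed correlations and early-visit SDs.

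A reader might infer more than the documents support:
- **That the false-positive rate is about 9%.** That figure applies only if visits are compared one at a time, which for AUC appears only in the power statement. Moreover, rejections exceed 5% only if supplementation changes spread but not mean. If it affects nobody, the arms have equal variance and the test is valid. Otherwise the harm is interval miscoverage.
- **That placebo is shown to be more variable.** Equal SDs are not excluded.
- **That 2:1 or the power is wrong.** The stated power is reproduced. DHA level has no pilot SD, and 2:1 may still help the DHA-level regressions, so that part of the rationale is not judged.

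This is a cheap improvement, between optional and mildly recommended.

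**What to change.** For maternal cortisol AUC_I, prespecify:

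1. Across visits, a mixed model with group, visit and group-by-visit, an unstructured covariance estimated separately in each arm, and Kenward-Roger or Satterthwaite degrees of freedom, in place of the rmANOVA.
2. For any single-visit contrast, Welch's test, or HC3 standard errors when covariates are included.
3. The data sets: the same intention-to-treat sets as the rmANOVA it replaces, with LOCF as the main analysis and complete cases as sensitivity, as in the Missing data section.
4. A fallback if the arm-specific covariance does not converge: Welch's test on each woman's mean AUC for group, and robust standard errors for group-by-visit.
5. A reworded Participants paragraph, so that the variance argument for 2:1 rests on DHA level or other stated grounds and not on stress reactivity.

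Allocation, sample size, blocking and blinding are unchanged.

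**Cost.** SAP wording and one covariance option. With equal SDs the power loss is under 1 point (at most 0.3 for group, 0.8 for group-by-visit with Kenward-Roger). If pilot SDs hold, with a 3.6 difference at the last one or two visits, the group effect loses 1.7-5.3 points, because the rmANOVA is then running above 5%, and group-by-visit loses 0-3.3 points. At a single visit Welch's test keeps 97.4% against 98.7% for the pooled test under the same SDs, so the power statement survives.

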Identifying factors that can potentially interrupt this cycle has significant implications for public health. Growing evidence indicates that DHA supplementation improves maternal stress reactivity during pregnancy and protects neurodevelopment of the offspring, especially in the context of high levels of stress exposure. We propose a program of research that aims to translate such findings to address the significant health disparities for African American women and children. In the following section we present preliminary evidence for the efficacy of prenatal fatty acid supplementation on maternal perceived stress and stress reactivity in this high-risk population.

Preliminary support for hypotheses

We recently completed the first randomized controlled trial of DHA supplementation among pregnant African American women living in stressful, low-income, urban environments (for a full report see Keenan et al., in press, *Obstetrics & Gynecology*). Sixty-four pregnant women were recruited from the Obstetrics Clinics at the University of Pittsburgh. Inclusion criteria were: African American race, age between 20 and 30 years, 16-21 weeks of gestation, Medicaid insurance or Medicaid eligible, and low levels of DHA consumption as defined as less than two fish servings per week. Exclusion criteria were medical complications (e.g., gestational diabetes, pre-eclampsia), regular use of steroid medications, use of blood thinners or anti-coagulants, use of psychotropic medications, current BMI >40, and allergy to iodine and/or soy. Participants were reimbursed on an accelerated schedule with \$40 for their first visit and an increase in payments of \$10 for each subsequent visit. The Institutional Review Boards of the Universities of Chicago and Pittsburgh approved all study procedures. Once enrolled, women were randomly assigned to receive the omega-3 nutritional supplement (n = 43) or a corn and soybean oil placebo (n = 21) beginning at enrollment and up through the end of pregnancy. Women received supplement via two gel capsules providing: 450 mg of DHA; 40 mg of docospentaenoic acid (DPA) and eicosatetranoic acid

[figure not shown]
(ETA); 90 mg of eicosapentaenoic acid (EPA); and 15 IU of Vitamin E. Randomization was conducted by the pharmacy at the University of Pittsburgh, thus ensuring that participants and investigators were blinded to the group to which the participants were assigned.

[figure not shown]

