In addition to associations between DHA supplementation and prenatal stress, we observed significantly higher birth weights among neonates born to women receiving DHA compared to placebo controlling for gestational age (3,174 grams versus 2,889 grams, p = .018) and greater likelihood of having a 1-minute Apgar score of 9 (odds ratio = 5.99 [95% Cl = 1.25 - 28.75], p = .025, controlling for birth weight and gestational age). Finally, 13% of neonates of mother receiving DHA supplementation were born prior to 37 weeks, compared to 22% of mothers received placebo; a difference that did not reach the level of statistical significance in the pilot study, but is clinically meaningful.

In summary, the data from our preliminary study are compelling in terms of the potential impact on health disparities in maternal and infant health, a significant public health problem that is poorly understood. We now seek to expand on these preliminary findings by conducting a more rigorous assessment of prenatal DHA supplementation on maternal and infant health by increasing the number of participants to 162, beginning supplementation earlier in pregnancy, adding additional measures of maternal health and stress response during pregnancy, increasing the frequency of assessment, assessing DHA levels in red blood cells at each visit, and including multiple postnatal assessments of infant neurodevelopment. The proposed study offers an opportunity for replication and to test the impact of supplementation on infant functioning and, if effects are observed, whether they are mediated by changes in prenatal stress.

APPROACH

Participants

One hundred-sixty-eight pregnant, African American, women will be recruited from the University of Chicago obstetric clinic. Inclusion criteria will include: age between 18 and 34 years, household receipt of public assistance (e.g., Medicaid insurance) due to low-income, and low levels of DHA consumption as defined as less than two fish servings per week. Exclusion criteria are reports of known medical complications, regular use of steroid medications, alcohol, cigarettes, or illegal substances (by maternal report), use of blood thinners or anti-coagulants, use of psychotropic medications, BMI >40, and allergy to iodine and/or soy. Participants may be excluded if medical complications arise after enrollment. Neonates with significant medical complications will be maintained in the study.

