-20 -5 +20 +40 +50 saliva saliva saliva saliva saliva 2 3 5 Consent & Instrumentation BP (x4) BP (x1) BP (x1) BP (x1) BP (every 5 minutes) HR (x 4) HR (x 2) HR (x 2) HR (x 2) HR (every 5 minutes) Questionnaires, supplement distribution, **Baseline Prepare** Speech Math Snack **Blood Draw** scheduling (20 min) (3 min) (3 min) (3 min) (5 mins) (10 mins) (50 min)

Figure 5. Protocol for prenatal laboratory visits

Methods

All visits will take place in the Department of Psychiatry and Behavioral Neuroscience at the University of Chicago. All prenatal visits will follow the same protocol (see Figure 5). Participants will provide a saliva sample upon arrival to the laboratory and an occluding cuff will be placed on the non-dominant arm for automated measurement of BP. A 3-lead electrocardiogram (ECG) will be attached to the shoulders and xyphoid process for continual measurement of heart rate. Following instrumentation, there will be a period of acclimation during which they will rest quietly while viewing a non-stressful video at the end of which a second saliva sample will be obtained. This will be followed by administration of the Trier Social Stress Test (TSST). Participants will complete psychosocial stress questionnaires following the TSST. These questionnaires will cover perceived stress, stressful life events, and symptoms of anxiety and depression. Following the final saliva sample, participants will be provided with a snack and then will be accompanied to the Clinical Research Center (which is located two floors above our laboratory) for the blood draw which will be used to assess DHA levels and inflammatory markers (C-reactive protein (CRP); IL-6; TNF-α).

Offspring stress reactivity will be measured via behavioral and cortisol response to the Brazelton Neonatal Behavioral Assessment Scale (NBAS) at 1 month and in response to the Face-to-Face Still-Face (FFSF) paradigm at 4 and 9 months. Infant cognitive development and behavior and emotion regulation during developmental testing also will be assessed.

Nutritional Supplement. As in the pilot study, the nutritional supplement we propose to use is ProDHA. The same dose will be used, with 2 gel capsules providing: 450 mg of DHA; 40 mg of DPA and ETA; 90 mg EPA; and 15 IU Vitamin E.

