Nordic Naturals adheres to high standards on safety and purity by setting low levels of allowances for peroxides, heavy metals, dioxins, furans, and PCBs. A certificate of analysis is provided for every batch of ProDHA based on both an internal analysis and an analysis conducted by an independent laboratory.

The investigational pharmacy at the University of Chicago will use computer generated random assignment of ID numbers to active supplement or placebo in blocks of 18: 12 ID numbers will be randomized to active supplement and six to placebo. In order to maintain the double-blind, the pharmacist will divide each randomization block of 18 ID numbers into groups of three: six ID numbers were assigned to group A (placebo) and the remaining 12 will be assigned to either group B or C, both of which will receive identical doses of active supplement. This approach will allow the pharmacist to randomize on a 2:1 ratio without having the unbalanced design break the blind. Once the study is complete and the blind broken, the two groups receiving identical doses of active supplement will be combined for analyses.

Each participant will receive a 6-week supply. She will bring any unused DHA back to her next visit; pills will be double counted at that time as an additional method for monitoring compliance. At each visit she will receive the next supply. Research assistants will contact participants by phone 3 times per week to ask the time of day that supplement was taken, and data on perception of taste, and possible gastrointestinal side effects. At each laboratory visit research assistants will interview participants about diet over the past 24 hours and past two weeks to determine intake of sea fish or other DHA rich foods (e.g., flax seed).

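### Six-week supplies handed out only at visits cannot cover the 14 to 20 weeks between the 16-20 and 34-36 week visits

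*Combined protocol and SAP*

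**What the plan says.** The Nutritional Supplement paragraph under Methods states one quantity: "Each participant will receive a 6-week supply". On returns it says "She will bring any unused DHA back to her next visit", where capsules are counted to monitor compliance, and then "At each visit she will receive the next supply". It does not give the size of that next supply or say whether returned capsules go back to the participant. Figure 5 makes dispensing part of the prenatal laboratory visit ("Questionnaires, supplement distribution"). Between visits the only supplement-related contact described is by telephone: "Research assistants will contact participants by phone 3 times per week to ask the time of day that supplement was taken".

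The Participants section sets the intended dosing period as "beginning at enrollment and up through the end of pregnancy". Table 1 heads three prenatal columns 16-20, 24-30 and 34-36 weeks. The Maternal Inflammatory Markers paragraph counts four prenatal visits. The fourth is the baseline visit, whose column heading is not legible in the text available. The end of the pilot section says the new trial will differ from the pilot by "beginning supplementation earlier in pregnancy"; the pilot enrolled at "16-21 weeks of gestation".

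**The concern.** Followed as written, the dispensing rule does not fit the visit schedule. The visits are further apart than two 6-week supplies can bridge, so a woman who takes every capsule runs out before at least one of her next two visits. That conflicts with supplementation through the end of pregnancy.

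The timing matters because the gap falls directly before an assessment. The last prenatal visit provides the maternal stress mediator in Hypothesis 3, the end point of the regression of perceived-stress change on DHA change in Hypothesis 1, and one of the DHA levels related to infant outcomes in Hypothesis 2. An unplanned interruption on active supplement could weaken the contrast with placebo at these points. The group-by-visit interaction for the cortisol AUC is also meant to show whether the difference depends on length of supplementation. Visit would still order cumulative exposure, but 14 to 20 elapsed weeks would carry only 10 to 12 weeks of product. The capsule count would not reveal the problem: a woman who has run out returns nothing, which looks like full compliance.

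**Working it through.** The plan states no coverage figure, so there is none to reproduce. The check is interval arithmetic on the visit windows.

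**Inputs**
- Supply: 6 weeks per dispensing (Nutritional Supplement). That later supplies are also 6 weeks is an inference.
- Visit weeks (Table 1): v2 from 16 to 20, v3 from 24 to 30, v4 from 34 to 36.
- Number of visits: four prenatal (Maternal Inflammatory Markers). The payment schedule agrees: payments rise from $100 to $250 in $25 steps, so (250 − 100)/25 + 1 = 7 visits, four prenatal and three postnatal. The unlabelled prenatal column stands before 16-20 weeks, so no extra dispensing falls between v2 and v4.

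**Span and supply**
- Shortest span: 34 − 20 = 14 weeks. Longest: 36 − 16 = 20 weeks.
- Supplies given at v2 and v3: 2 × 6 = 12 weeks at most.
- Hence at least 14 − 12 = 2 weeks are uncovered.

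**Without re-issue of leftovers**

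Weeks without product = max(0, v3 − v2 − 6) + max(0, v4 − v3 − 6).
- Minimum, for example visits at 20, 26, 34: 0 + 2 = 2 of 14 weeks (14%).
- Window midpoints 18, 27, 35: 3 + 2 = 5 of 17 weeks (29%).
- Maximum, for example visits at 16, 24, 36: 2 + 6 = 8 of 20 weeks.
- Product actually used between v2 and v4: 10 to 12 weeks. The 10 arises with visits at 16, 30, 34, where 6 + 4 = 10.

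There are 5 × 7 × 3 = 105 whole-week combinations, and none is fully covered:

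| Gap falls | Combinations |
|---|---|
| only before the 24-30 week visit | 30 |
| only before the 34-36 week visit | 18 |
| before both | 57 |

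So 30 + 57 = 87 leave a gap before the 24-30 week visit and 18 + 57 = 75 before the 34-36 week visit. These counts test the windows; they do not forecast when women will attend.

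**With every leftover re-issued**

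Each visit now adds 6 weeks to whatever stock remains. Three supplies (baseline, v2, v3) give 18 weeks, so a zero gap needs v4 − b ≤ 18, where b is the baseline week. With v4 at its earliest, b must be at least 34 − 18 = 16. Because the baseline heading is not available, b is varied as an assumption, with b before v2:

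| Baseline week b (assumed) | Total gap from b to v4, weeks | Combinations with no gap |
|---|---|---|
| 12 | 4 to 6 | 0 of 105 |
| 13 | 3 to 5 | 0 of 105 |
| 14 | 2 to 4 | 0 of 105 |
| 15 | 1 to 3 | 0 of 105 |
| 16 | 0 to 2 | 20 of 84 |
| 17 | 0 to 1 | 36 of 63 |
| 18 | 0 | 42 of 42 |

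At the window midpoints the gap with re-issue is 0 + 3 + 2 = 5 weeks from b = 12, 0 + 1 + 2 = 3 from b = 14, and 0 + 0 + 1 = 1 from b = 16.

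**The two ends of the schedule**
- The first supply reaches week 20, the end of the next window, only if baseline is at week 20 − 6 = 14 or later.
- The last prenatal supply reaches week 34 + 6 = 40 to 36 + 6 = 42, which is adequate.

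**The case against.** The strongest reply is that the shortfall is conditional. The plan does not size the later supplies or rule out re-issue, and a reader could take the stated aim of dosing to the end of pregnancy as governing, with each supply large enough to meet it. This is also a research plan, and dispensing quantities may be left to the investigational pharmacy. The conditional nature stands and limits confidence. Even so, 6 weeks is the only quantity given and repeating it is the natural reading. Nothing describes larger later supplies, re-issue or resupply between visits.

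A second point is that calls three times a week should expose a run-out within days, and small incentives already reach participants between visits. Detection is likely, but the plan attaches no action to it.

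Third, the harm is unproven. An interruption would strike both blinded arms, so it would tend to weaken an effect rather than create one. Red-cell DHA is measured at all four prenatal visits, and average DHA is an alternative exposure variable in Hypothesis 3. All of this is fair. Those measurements would show low exposure, but they would not restore the randomised comparison.

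Fourth, the re-issue results depend on a baseline week that cannot be seen. That is why they are given as a range. The result without re-issue does not depend on it.

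**Conclusion.** The concern holds, with medium confidence. On the natural reading, with 6 weeks per supply and no re-issue, every schedule within the Table 1 windows leaves a fully adherent woman without product for 2 to 8 weeks between the 16-20 and 34-36 week visits. Full re-issue removes the gap for certain only from a baseline at week 18, and never for a baseline before week 16. The closer the trial keeps to its aim of starting earlier than the pilot, the larger the shortfall under re-issue. The conclusion would fall away if later supplies are sized to the visit interval or sent between visits, but the plan says neither. The dilution at the later visits cannot be calculated. This should be fixed before dispensing starts, because it affects delivery of the intervention directly before key assessments.

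**What to change.** State the quantity dispensed at each prenatal visit and whether returned capsules are re-issued. Then make the quantity fit the schedule in one of two ways.

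- **Dispense to the end of the next visit window:** from baseline to week 20; up to 30 − 16 = 14 weeks at the 16-20 week visit; up to 36 − 24 = 12 weeks at the 24-30 week visit. The supply given at 34-36 weeks needs little change.
- **Keep 6-week supplies and add resupply between visits**, triggered when the existing phone calls show that stock is nearly finished.

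The cost is protocol wording plus either somewhat more product per dispensing or modest resupply logistics. Clarifying the quantity without changing it would not be enough if it is 6 weeks throughout.
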